4.7. Assessment of safety

All adverse events will be recorded, intervened according to medical assessment, and monitored. Participants are asked open-ended questions about how they have been feeling in general and if they have any concerns regarding their health or the study medication. The DSMB will review the study reports and determine any safety issues if they arise.

4.8. Assessment of predictors and moderators

- The Standardised Assessment of Personality Abbreviated Scale (SAPAS) will be used to identify those with suspected personality disorders and this will be used as a covariate in the analysis and also used as a variable of interest in examining treatment response.
- The Dietary Questionnaire for Epidemiological Studies Version 2 (DQES v2) is a self-administered paper based modification of the food frequencies questionnaire developed by the Cancer Council to measure dietary intake. Diet quality can then be used as a covariate in the analysis and also used as a variable of interest in examining treatment response.
- Analysis of biomarkers of oxidative and inflammatory markers will be used to determine how treatment response (if present) correlates to changes in biological markers.
- Changes in biomarkers will be used to explore the underlying pathophysiology of depression.

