6.6. Randomisation

After the baseline assessment has been completed, the participant will be randomised to either the *Garcinia mangostana* Linn group or the placebo group. Allocation to treatment arm will be randomly assigned in a 1:1 ratio (active to placebo) using permutated block randomisation. An independent researcher utilising a four-to-a-block design will develop the computer-generated randomisation plan. Trial clinicians will allocate packs sequentially, and bottles are identical so as to conceal treatment allocation and blinding. To facilitate the double-blinding process, the trial medications will be dispensed by an independent pharmacist in identical numbers and capsule forms in sealed containers. The statistician and trial clinicians will be blinded to the group allocation.

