9.2. Method of statistical analysis

All analyses will be conducted in accordance with the International Conference on Harmonization E9 statistical principles, and are based on all randomised participants with at least one post-baseline observation (intention to treat population). Reporting of research findings will be done in accordance to CONSORT guidelines. The statistician responsible for the analysis of outcome data will be blind to group allocation. The primary efficacy analysis will assess average treatment group differences for the primary outcome measure MADRS total score over the entire study period and will use a likelihood based mixed-effects model, repeated measures approach (MMRM). The MMRM model includes the fixed, categorical effects of treatment, investigator, visit, and treatment-by-visit interaction, as well as the continuous, fixed covariates of baseline score and baseline score-by-visit interaction. The MMRM includes all available data at each time point and is the preferred method of analyzing clinical trial data in psychiatry as compared to more traditional repeated measures analysis of variance (ANOVA) and analysis of covariance models (ANCOVA). Planned comparisons will be done with the MMRM models to determine between group differences in change of symptoms measures from baseline to week 24. Results from the analysis of dichotomous data will be presented as proportions, with 95% confidence interval, and Fisher's exact p-value where appropriate. Non-parametric statistics will be used when assumptions for parametric methods are violated. Effect sizes will be calculated using Cohen's guidelines. All tests of treatment effects will be conducted using a two-sided alpha level of 0.05 and 95% confidence intervals. Change scores in symptoms and in biological markers will be derived. Pearson Product Moment Correlations will be used to examine the relationships between the change scores for symptoms and the change scores for biological markers in the two groups. Using Fisher's z transformation, we will test whether the correlations obtained for each group are statistically different in terms of strength.

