9.3. Sample size and power

We are aiming for a target sample size of 150 participants. For a two tailed analysis with α =0.05, $Z\alpha$ = 1.96 and with β =0.2, $Z\beta$ = 0.8, N=120, the study should be powered at 80% to detect a true difference in MADRS scale score between the mangosteen pericarp and placebo groups if the effect size is

Cohen's *d*=0.362 or greater. This is a conservative estimate, based on the results of the pilot data. However, in our previous trial of N-acetylcysteine specifically investigating bipolar depression, effect sizes for depressive symptoms (BDRS, MADRS), clinical global impression of depressive severity (CGI BP-depression), as well as all functional measures have shown effects similar to or above the effect size the sample has been calculated for. Based on our previous trials we typically have an attrition rate of 20%. Therefore, although power calculations indicated 120 participants will be sufficient to detect between group differences, we plan to recruit 150 participants to account for attrition.

10.Ethics

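### Section 4.8 appears to reduce SAPAS to a suspected-personality-disorder grouping, which would weaken the exploratory moderator analysis; the score should enter as a continuous variable

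*Protocol*

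**What the plan says.** Protocol section 4.8 gives SAPAS two roles. It "will be used to identify those with suspected personality disorders and this will be used as a covariate in the analysis", and it is "also used as a variable of interest in examining treatment response". The section gives no cut-off, score range, scoring rule or expected share of participants with a suspected disorder. Table 1 schedules SAPAS once, at baseline.

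The next bullet in section 4.8, on the dietary questionnaire, is worded differently: "Diet quality can then be used as a covariate in the analysis". That names a quantity and sorts nobody into groups.

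Section 9.2 lists the terms of the primary mixed model: treatment, investigator, visit and treatment-by-visit, "as well as the continuous, fixed covariates of baseline score and baseline score-by-visit interaction". SAPAS is not among them. None of the hypotheses in sections 3.1.2 and 3.1.3 concerns SAPAS, so its use as a moderator is exploratory.

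**The concern.** In the SAPAS sentence the scale first identifies a group, and what then serves as covariate and moderator is most naturally that identification. The contrast with the diet bullet supports this reading. So does section 9.2, where the authors call a covariate continuous when they mean one.

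A two-way split of a scored scale treats everyone on one side of the cut as equal and makes participants just either side of it different. The result also depends on a cut that the protocol does not give. The harm falls on the treatment-by-SAPAS interaction. An interaction test is weak at this sample size in any case, and a null result from a split moderator could be misread as evidence that personality pathology does not affect response.

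**Working it through.** **1. The plan's own figure.** The protocol gives no number for SAPAS. Its only power statement, in section 9.3, concerns the main treatment effect: "N=120, the study should be powered at 80% to detect a true difference in MADRS scale score", for "Cohen's *d*=0.362 or greater". The two-sided 0.05 level is from section 9.2.

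- Required per arm: 2 × (1.960 + 0.842)² / 0.362² = 119.8, so 120 per arm.
- With 120 in total (60 per arm): power = Φ(0.362 × √(60/2) − 1.960) = Φ(0.023) = 51%.

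The stated figure therefore reproduces only if 120 is per arm. That is a separate matter and is not needed below.

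**2. Information kept by a split.** Assume a roughly normal score and a linear effect. The share of the score's linear information that a two-group split keeps is the squared correlation between the score and the split:

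r = φ(c)² / [p(1 − p)], where p is the share above the cut c.

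| Share above cut (assumed) | Kept, r | Lost |
|---|---|---|
| 50% | 0.3989² / 0.25 = 0.637 | 36% |
| 30% | 0.3477² / 0.21 = 0.576 | 42% |
| 25% | 0.3178² / 0.1875 = 0.539 | 46% |
| 20% | 0.2800² / 0.16 = 0.490 | 51% |
| 10% | 0.1755² / 0.09 = 0.342 | 66% |

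**3. Sensitivity to the score's shape.** The same squared correlation was computed for an assumed integer score from 0 to 8 (binomial and beta-binomial shapes, assumed cuts at 3 and 4). With 20% to 80% above the cut, the loss is about 25% to 45%. Taking these shapes and the normal case together, with at least 10% of participants on each side, the loss runs from about 25% to 66%.

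**4. Effect on a moderator test.** Treatment is randomised independently of SAPAS, so the noncentrality of the interaction test shrinks by √r. Start from a moderator effect that the full score would detect with 80% power:

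power = Φ[(1.960 + 0.842) × √r − 1.960]

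- r = 0.637: Φ(2.236 − 1.960) = 61%
- r = 0.539: Φ(2.057 − 1.960) = 54%
- r = 0.490: Φ(1.961 − 1.960) = 50%

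**5. Effect on covariate adjustment.** If the score correlates ρ with the outcome, the required N rises by the factor (1 − rρ²) / (1 − ρ²) when the split replaces the score.

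- ρ = 0.1, r = 0.64: 0.9936 / 0.99 = 1.004
- ρ = 0.3, r = 0.49: 0.9559 / 0.91 = 1.050

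Over assumed correlations of 0.1 to 0.3, that is about 0.4% to 5% more participants.

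**The case against.** **The text never says that the variable is binary.** The word after the conjunction could refer to the scale itself, and no cut-off is given. This stands: the grouping is the more natural reading, not a stated fact. If the authors meant the score, the same one-line clarification settles it.

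**Coding belongs in the SAP.** The SAP was not available for this review, and a cut-off could properly be left to it. The point here is not an omission: section 4.8 already indicates a form for the variable, and the one indicated is the weaker.

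**The size rests on assumptions.** This stands. Shape, linearity and split are all assumed, and if response truly changes at a threshold matching the cut, the split need not lose that information. Asking whether people with a suspected disorder respond differently is also a legitimate clinical question, and the grouping can still be used to display it.

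**The 80% starting point is only an illustration.** Section 9.3 powers no moderator test. From an assumed 30% power, a 36% loss gives Φ(1.436 × 0.8 − 1.960) = 21%. The test would be weak under either coding, so the fix makes it less weak rather than adequate.

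**Confounding.** A reader might infer that a coarse SAPAS covariate leaves residual confounding in the treatment comparison. It does not. Section 6.6 randomises 1:1, so a baseline score does not confound that comparison, and coarser adjustment costs only the slight precision shown in step 5 of the working.

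**Conclusion.** The point holds as a minor one about an exploratory analysis. On its most natural reading, section 4.8 makes covariate and moderator out of a suspected-disorder grouping with an unstated cut. If the score is split, the moderator analysis loses about 36% to 51% of the information, given a roughly normal score, a linear effect and 50% to 20% above the cut. Other assumed shapes and splits give about 25% to 66%. At the 36% to 51% losses, 80% power on the full score becomes about 61% to 50%.

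A reader might go further in two ways that the protocol does not support. One is to quote a loss of a third to a half as a property of this trial; without a cut-off, score range or distribution it is only a conditional range. The other is to conclude that the primary result is weakened; SAPAS is not in the section 9.2 model, so this is not shown.

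**What to change.** In section 4.8, state that the SAPAS total score enters as a continuous variable in the treatment-by-SAPAS interaction and wherever it is used as a covariate. Keep the suspected-disorder grouping for description and display, and state its cut-off there or in the SAP. If the SAP already enters the score as continuous, only the wording of section 4.8 needs to be aligned with it.

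The cost is a wording change. SAPAS is already collected at baseline, and no visit, measure or participant is added. The small downside is the assumption of a linear effect, which can be checked with a quadratic term. Settling this before unblinding also removes any discretion over where the cut falls.

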4.9. Exploration of biological correlates

Blood samples will be obtained at baseline and week 24, to be stored and later analysed for biological correlates based on preclinical evidence including markers of antioxidant defence (including antioxidant levels), oxidative stress (including markers of lipid peroxidation and protein carbonylation), and markers of inflammation (including IL1, IL6, CRP and $TNF\alpha$), which interact with oxidative stress.

Table 1: Instruments / procedures to be implemented at each study visit:

| VISIT | 1 | 2 | 3 | 4 | 5 | 6 | 7 | 8 |
|---------------------------------|-----------|------------|------------|------------|------------|------------|---------|-----------------|
| | Baseline/ | Interim | Interim | Interim | Interim | Interim | Primary | Post- |
| | Screening | assessment | assessment | assessment | assessment | assessment | End- | discontinuation |
| | * | | | | | | point | follow-up |
| WEEK | 0 | 4 | 8 | 12 | 16 | 20 | 24 | 28 |
| SCREENING AND CONSENT | | | | | | | | |
| Informed consent | Х | | | | | | | |
| Inclusion/exclusion criteria | X | | | | | | | |
| Demographics | X | | | | | | | |
| Medical history | X | | | | | | | |
| Psychiatric and family history | X | | | | | | | |
| Concomitant medication | X | Χ | Χ | X | X | X | Х | X |
| Pregnancy test (females only)** | X | | | | | | | |
| SCID-5-RV | X | | | | | | | |
| SAFETY | | | | | | | | |
| Adverse Events | X | Χ | Χ | X | X | X | Χ | X |
| EFFICIACY | | | | | | | | |
| MADRS | X | X | Χ | X | X | X | Х | Χ |
| BDRS | Х | Χ | Χ | X | X | X | Χ | Χ |
| YMRS | Х | Χ | Χ | X | X | X | Χ | Χ |
| HAM-A | X | Χ | Χ | X | X | X | Х | X |
| CGI-S | X | X | X | X | X | X | Χ | Χ |
| CGI-I | | Χ | X | X | X | X | Χ | Х |
| PGI | | Χ | Χ | X | X | X | Χ | X |
| COGNITION | | | | | | | | |
| Digit span forwards | X | | | | | | Χ | |
| Digit span backwards | X | | | | | | Χ | |
| Trail making | X | | | | | | Χ | |
| Symbol digit task | X | | | | | | Х | |
| FUNCTIONING AND QUALITY OF LIFE | | | | | | | | |
| Q-LES-Q | Х | X | X | X | X | X | Χ | Χ |
| SOFAS | X | X | Χ | X | X | X | Χ | Χ |
| LIFE-RIFT | X | Χ | Χ | X | X | X | Х | Χ |
| ASSESSMENT OF PREDICTORS AND | | | | | | | | |
| MODERATORS | | | | | | | | |
| SAPAS | Х | | | | | | | |
| DQES V.2 | X | | | | | | | |
| HEALTH ECONOMICS | | | | | | | | |

| VISIT | 1 | 2 | 3 | 4 | 5 | 6 | 7 | 8 |
|----------------------------------|-----------|------------|------------|------------|------------|------------|---------|-----------------|
| | Baseline/ | Interim | Interim | Interim | Interim | Interim | Primary | Post- |
| | Screening | assessment | assessment | assessment | assessment | assessment | End- | discontinuation |
| | * | | | | | | point | follow-up |
| AQOL-4D | X | | | X | | | Χ | |
| HEALTH UTILISATION QUESTIONNAIRE | X | | | X | | | Χ | |
| EXPLORATION OF BIOLOGICAL | | | | | | | | |
| CORRELATES | | | | | | | | |
| Blood specimen | Х | | | | | | Х | |
| OTHER | | | | | | | | |
| Drug Dispensation | Х | Х | Х | Х | Х | Х | | |

^{*} Baseline and screening interviews may be split to accommodate participant time.

^{**}If participant is not sexually active or the treating clinician feels it is not warranted, this is not compulsory.

5. Study Design and Plan

5.1.Setting

The study will be conducted at The Melbourne Clinic and Albert Road Clinic in Melbourne, Barwon Health in Geelong and Toowong Clinic in Brisbane. Sponsorship for the study will be provided by Barwon Health. The teams at all recruiting sites have strong links with established clinical trial teams with track records in innovation including partners on the pilot trial.

5.2.Sample

Participants will be sought from private and public healthcare settings as well as community recruitment. Participants (N=150) aged 18 and above years with moderate to severe bipolar depression will be studied. Participants must meet the DSM-5 criteria for bipolar disorder I or II, or bipolar disorder not elsewhere classified (NEC), determined using the Structured Clinical Interview for DSM Disorders (SCID-5-RV), meeting criteria of a Montgomery Asberg Depression Rating Scale score of ≥20 and current major depressive episode on the SICD-5. The participants will be assigned randomly and consecutively to treatment with mangosteen pericarp or placebo in a double blind fashion in addition to treatment as usual (TAU). All participants will remain on their usual treatment for the course of the trial.

5.3. Study Design

This is a 24-week, double blind, randomised, placebo-controlled trial of adjunctive *Garcinia mangostana* Linn in the treatment of bipolar depression (n=150). The duration of the current trial will be 24 weeks concordant with our pilot data. A follow-up interview will be scheduled 4 weeks after completion of the study. The trial will be conducted following approval from the relevant ethics committees, and conducted in accordance with the Good Clinical Practice guidelines. The trial will be conducted according to Australian Clinical Trial guidelines and the National Ethical guidelines for Human Research. This protocol was developed in accordance with Standard Protocol Items Recommendations for Intervention Trials (SPIRIT) 2013 guidelines, and findings will be reported using CONSORT guidelines. All participants will give informed consent prior to enrolment. Participants will be withdrawn from the study if they withdraw consent or at the discretion of the investigators.

6. Procedure

6.1. Identifying potential participants

All sites have a clinical trials teams dedicated to the successful conduct and completion of clinical trials in psychiatric disorders. We have established protocols for maximising recruitment and retention rates. We utilise various recruitment avenues including advertisement through local newspapers, flyers in medical waiting rooms, pharmacies and university campuses, and direct contact with potential referral sources. These consist of general practitioners, community mental health teams, the disability support sector, support groups, private psychiatrists and the local psychiatric inpatient unit.

Participants contact the trials team directly via the mangosteen email, by calling local clinicians directly (details on all promotional materials), may be forwarded on through Healthshare – an online health portal, contacted through our centralized database, or may be encouraged by treating mental health professionals to contact the trials team. Participants may also be contacted following referral from their treating physician and will be informed that they are being offered the study through that channel.

6.2. Obtaining informed consent

Participants who are deemed competent to provide informed consent will be included in the study. This competency will be determined by the researcher, in collaboration with the treating physician if required, and will take into consideration a broad range of factors as suggested within the NHMRC *National Statement* on Ethical Research in Humans.

6.3. Revocation of informed consent

All participants have the right to revoke consent from the study at any time and this must be clearly stipulated at the time of consent. Participants may request to have their blood sample destroyed at this time. Revocation of consent forms will need to be completed for all participants (where possible) who withdraw from the study. Revocation of consent will refer to the destruction of clinical data. This is independent of withdrawal of consent, where a participant may choose to withdraw from the study, but have their data used regardless.

6.4. Screening assessment

No study specific procedures or investigations will be performed before the participant has signed and dated the informed consent form. After consent has been obtained, a research assistant will conduct the screening assessment as per Table 1. This will include a full assessment of all inclusion and exclusion criteria. In the event that face-to-face recruitment is not possible due to safety concerns, we will alter recruitment to utilise online methods including Zoom, Skype, or teleconference as a last resort. If screening via an online method, participants will not be asked to provide blood specimens. Participants will be provided with the PICF either in hard copy or electronically, as they prefer. Once received, the participants will have the opportunity to review the information and discuss with anyone they deem relevant. The researcher will review the PICF document over the telephone or via an online medium with the participant and establish consent. Participants either will be able to sign the PICF and return electronically or will be provided with a reply paid envelope to mail hardcopy documents back to the researcher for sighting and archiving. If the participant does not meet one of the requisite inclusion criteria, they will not take further part in the trial. For example, if the initial assessment reveals that a participant does not actually meet a diagnosis of bipolar disorder I or II, or bipolar disorder not elsewhere classified (NEC), or that their MADRS score is lower than 20, or they do not meet current major depressive episode on the SCID-5-RV, then they will be withdrawn based on the fact that they do meet inclusion criteria. These participants will be deemed to be 'screen fails' and will be constituted as such in the CONSORT flowchart.

6.5. Biological correlates

For consenting participants, blood samples will be obtained at baseline and week 24 and will be stored and later analysed for relevant markers based on preclinical evidence including markers of antioxidant defence (including antioxidant levels), oxidative stress (including markers of lipid peroxidation and protein carbonylation), and markers of inflammation (including IL1, IL6, CRP and TNF α) and a range of other sera markers related to general health, which interact with oxidative stress. Participants will have the option to consent to the collection of blood samples to explore RNA expression. We will explore the expression of genes that may be influenced by mangosteen pericarp including metabolic, oxidative, inflammatory and cell cycle genes. For consenting participants, the RNA sample will be collected using PAXGene Blood RNA tubes. In addition to these analyses, Participants will have the option to give unspecified consent for future research. Any future studies will be conducted after approval from a Human Research Ethics Committee. All bloods will be stored in -80°C Freezers for no more than 15 years.

6.6. Randomisation

After the baseline assessment has been completed, the participant will be randomised to either the *Garcinia mangostana* Linn group or the placebo group. Allocation to treatment arm will be randomly assigned in a 1:1 ratio (active to placebo) using permutated block randomisation. An independent researcher utilising a four-to-a-block design will develop the computer-generated randomisation plan. Trial clinicians will allocate packs sequentially, and bottles are identical so as to conceal treatment allocation and blinding. To facilitate the double-blinding process, the trial medications will be dispensed by an independent pharmacist in identical numbers and capsule forms in sealed containers. The statistician and trial clinicians will be blinded to the group allocation.

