4.1. Study Procedure

Trial clinicians will contact all participants referred to the trial to schedule an initial face-to-face screening interview. During the initial interview, the trial clinicians establish written consent, that inclusion criteria are satisfied, and confirm the diagnosis using the (SCID-5-RV). All randomised participants will receive two 500mg mangosteen pericarp capsules once a day to a total dose of 1000mg daily (or placebo) with food, in addition to treatment as usual. The mangosteen pericarp and placebo will be encapsulated and matched in appearance. Dose changes to existing medications (either increases or decreases in dose) or switch in medication will be accepted, documented and participants will be allowed to continue on the trial.

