6.11. Blinding and unblinding the study

6.11.1. Methods for ensuring blinding

Blindness will be maintained by ensuring that the packaging, appearance, colour and taste of mangosteen pericarp and placebo capsules are identical. Blindness will also be maintained by the use of an anonymous Participant-ID and not allowing study personnel access to the randomisation code unless in an emergency. The research assistants will remain blinded throughout the entire trial. Analysis of the data will also be conducted blind to the statistician and Investigators.

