6.11.2. Methods for unblinding the study

Protocol: MANGO BD

Individual treatment codes, indicating the treatment randomisation for each randomised participant, will be available to the pharmacists at the participating sites. The treatment code must not be broken throughout the study period except in medical emergencies when the appropriate management of the participant necessitates knowledge of the treatment randomisation. All cases of emergency unblinding must be thoroughly documented and require reporting to the DSMB (if that had not occurred previously). Participants will be notified at the completion of all participants in the study, which arm of the study they took part in.

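### The protocol prints one fixed block size of four for the clinicians who hand out packs in sequence, so one emergency code break tells them something about the block-mates; the risk is small and the fix cheap

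*Protocol*

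**What the plan says.** Protocol section 6.6 has participants "randomly assigned in a 1:1 ratio (active to placebo) using permutated block randomisation". It continues: "An independent researcher utilising a four-to-a-block design will develop the computer-generated randomisation plan". No other block size is mentioned, and nothing says that the size is withheld from site staff. The same section states: "Trial clinicians will allocate packs sequentially, and bottles are identical so as to conceal treatment allocation and blinding". It also promises: "The statistician and trial clinicians will be blinded to the group allocation".

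Section 4.1 describes the same group at the point of entry: "Trial clinicians will contact all participants referred to the trial to schedule an initial face-to-face screening interview". At that interview they also obtain consent, check inclusion criteria and confirm the diagnosis.

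Section 6.11.1 protects the blind partly by "not allowing study personnel access to the randomisation code unless in an emergency". Section 6.11.2 leaves individual codes with the site pharmacists and forbids breaking them "except in medical emergencies when the appropriate management of the participant necessitates knowledge of the treatment randomisation". Each break must be documented and reported to the DSMB.

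**The concern.** Concealment in a blocked design depends on staff being unable to reason from one allocation to another. Here the block length is constant and is written in the document that trial clinicians work under, and those clinicians issue the packs in order. The stated safeguards (identical bottles and capsules, sealed containers, an independent list-maker, an independent pharmacist) hide what is in a pack. They do not prevent inference from one known code to the rest of its block, which may include people not yet enrolled.

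Entry requires a MADRS score of at least 20 (4.5.1), and the MADRS total is the primary outcome (4.4). Both rest on a rated scale, so a suspicion about allocation is the kind of information that the blinding in 6.6 is meant to keep from those who enrol and assess.

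**Working it through.** The protocol gives no figure for predictability, so there is none to reproduce.

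**Inputs.** Block size 4 and a 1:1 ratio (both 6.6). Codes may be broken one participant at a time in an emergency (6.11.2).

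**One code known, block boundary known.** A 2:2 block has C(4,2) = 6 equally likely sequences. If the known pack is active (A) and comes first, three remain: AAPP, APAP, APPA. In general, for block size b,

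P(a given block-mate is in the opposite arm) = (b/2)/(b − 1).

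- b = 4: 2/3 = 0.667, against 0.5 with no information.
- Guessing the opposite arm for all three block-mates is right for 3 × 2/3 = 2.0 of them on average, against 1.5 by chance.

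**One code known, block boundary unknown.** The known pack is taken as equally likely to be in any of the four positions, so the next pack is in the same block with probability 3/4:

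P(next pack opposite) = 3/4 × 2/3 + 1/4 × 1/2 = 5/8 = 0.625.

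**Two codes known in the same block.** They are alike in 2 of the 6 sequences (probability 1/3). The other two packs must then both be in the opposite arm, with certainty.

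**With undisclosed blocks of 4 and 6.** Assume that the two sizes are equally frequent. A pack then falls in a block of 4 with probability 4/10 and in a block of 6 with probability 6/10. For a known block of 6, the formula gives 3/5.

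- Block of 4: 3/4 × 2/3 + 1/4 × 1/2 = 0.625.
- Block of 6: 5/6 × 3/5 + 1/6 × 1/2 = 0.583.
- P(next pack opposite) = 0.4 × 0.625 + 0.6 × 0.583 = 0.600.

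After a single code the gain is modest: 0.600 against 0.625 (boundary unknown) or 0.667 (boundary known). The larger gain is that two like codes no longer settle the rest of a block.

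**Cost in balance.** A list that stops inside a block of size b can be out of balance by at most b/2: 2 for blocks of 4, 3 for a last block of 6. Some imbalance is possible already. On a single list, 150/4 = 37.5, so the target of 150 stops halfway through a block.

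**The case against.** The strongest reply is that the situation will seldom arise and that little is learned when it does. Capsules match in packaging, appearance, colour and taste (6.11.1). Pharmacists hold the codes, breaks need a medical emergency, and participants learn their arm only after everyone has finished (6.11.2). One break gives a likelihood and not an allocation. All of this stands and sets the size of the point.

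It also stands that nothing shows clinicians knowing where blocks begin. There are four sites, and the protocol does not say whether the list is central or per site. With a central list, block-mates could be scattered across sites. Roles are not clear-cut either: 4.1 gives the screening interview to trial clinicians, 6.4 gives the screening assessment to a research assistant, and 6.11.1 says that research assistants stay blinded throughout.

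Several stronger readings are tempting, but the documents do not support them:

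- A reader might compute predictability as if every earlier allocation in a block were known. That describes an open-label trial, and this design prevents it.
- A reader might take the SAE reporting text in 6.13.3 as a second route to unblinding. It only requires a further report if unblinding is needed.
- A reader might infer that ratings or background treatment will be biased. No text says that the person who learns a code also rates the MADRS. Participants must have their own treating physician (4.5.1, 6.15), and changes to background medication are not assigned to trial staff.

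None of this removes the inference from a known code to its block-mates.

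**Conclusion.** The point holds as a small, avoidable weakness in concealment. It is not a contradiction, and it does not show that the blind will fail. One broken code moves each block-mate from 1/2 to 2/3, or the next pack to 5/8 if the boundary is unknown. Certainty needs two like codes known to be from one block.

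This rests on three assumptions: that trial clinicians know the block size because it is in their protocol; that packs are issued in list order; and, for the 2/3 and the certainty, that block boundaries can be worked out. The expected number of code breaks is not given, so no bias in the treatment effect can be estimated. The case for acting is that the change costs little and closes off the certain deduction.

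**What to change.** Have the independent researcher generate the list, or the blocks not yet opened if it is already in use, with randomly varied block sizes, for example 4 and 6. Keep the sizes in a restricted randomisation document that site staff do not see. In section 6.6, replace the four-to-a-block wording with: *permuted blocks of varying, undisclosed size*. Rewording alone is not enough, because staff may already have read the current text.

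The cost is a small change to the list-generation program and one protocol wording change. If packs have already been made up to the present list, the unopened ones may need renumbering; the protocol does not say. The possible imbalance when recruitment ends rises from 2 to 3 per list. Whether to use separate lists by site is a different design decision, and this point does not call for it.
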